# 729 10 RCT Tests, Procedures and Participant Withdrawal

730 10.1 Procedural Summary

[figure not shown]
This RCT will utilize a 2 x 2 factorial design to evaluate the effectiveness of 1) placebo
plus placebo, 2) placebo plus Elmiron® 3) hydroxyzine plus placebo 4) hydroxyzine plus
Elmiron® in the improvement of moderate to severe symptoms of pain/discomfort and
frequency in IC participants. Approximately 136 participants with clinically diagnosed
moderate to severe IC will be recruited from eight clinical sites throughout the United
States.

Prior to baseline screening, potential participants must have been diagnosed with IC, confirmed sometime in the past with the results from a cystoscopy/hydrodistention.

739 This study is comprised of two distinct phases for each participant: i) the screening 740 phase and ii) the treatment and follow-up phase (Appendix G). The screening phase, 741 which assesses a participant's eligibility via inclusion, exclusion and deferral criteria, will 742 consist of two "baseline" visits no more than 4 weeks and no less than 7 days apart. Any 743 candidate failing any of the inclusion or exclusion criteria will be considered ineligible 744 for the protocol and treated according to usual clinical care. Some participants who 745 initially fail study entry criteria may later be reconsidered for inclusion if the 746 exclusionary conditions resolve (section 5.3-5.5). Any participant meeting all of the 747 criterion will then be eligible for randomization to one of the four treatment arms. After 748 randomization, participants are asked to return to the clinic for follow-up visits at weeks 749 3, 10, 17 and 24. Study medications will be dispensed at each clinic visit and participants 750 will be asked to complete several quality of life and symptom scale questionnaires. At 751 week 24, any participant requesting to continue on study medication will be provided 752 masked medication until the study is closed. These participants will be followed every 753 12 weeks.

- 754 755 756
- 757
- 758
- 759
- 700
- 760
- 761
- 762
- 763

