#### Figure 2. Treatment Design Schema

- 794 be instructed to remember his/her overall urinary symptoms on this day. He/she will be informed, that upon completion of the study, or withdrawal, whichever 795 comes first, he/she will be asked to compare the overall symptoms experienced 796 797 at Baseline Visit 2 to that at week 24. This visit must occur no less than 1 week 798 and no more than 4 weeks after the first baseline visit. In order to meet 799 eligibility criteria, the participant must report a voiding frequency of at least 11 800 times in a 24 hour day, and a pain/discomfort score of at least 4 at both Baseline 801 1 and Baseline 2 Visits (see all inclusion/exclusion/deferral criteria in Sections 802 5.3 to 5.5).
- 803If it is determined that the participant meets all eligibility criteria, then804randomization to one of the four treatment arms is implemented. Participants805will be stratified by randomization site and randomized in equal proportions to806one of the four treatment arms, using a randomized block design with varying807block sizes.
- 808 At the time of randomization, the participant will be provided with both study medications and thorough instructions on how to take each of them. The RC 809 810 must approve and document any changes in study medication dosages during the 3 week titration/dose stabilization for the green capsules. The following 811 questionnaires will also be administered: Symptom Ranking Cards, IC 812 Symptom & Problem Index, University of Wisconsin Symptom Survey, Health 813 Status Questionnaire (MOS SF-36), and the MOS Sexual Functioning Scale. In 814 addition, a urine sample will be collected, processed, frozen and shipped to the 815 Core Pathology Laboratory, for storage (Appendix H). In addition, the 816 817 participant will be asked to maintain a daily medication diary. This diary will be returned and replaced with another booklet at every clinic visit. 818

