#### 1141 15.3 Intent-toTreat Analyses and Missing Data

1142 An *intent-to-treat* analysis, in which all available data on all randomized participants are 1143 included, will be used for the primary comparison of treatments. All attempts will be 1144 made to keep missing data to a minimum and participants who withdraw from treatment will be encouraged to continue on study in order to provide complete follow-up 1145 information. However, it is expected that up to 30% of the randomized participants may 1146 1147 withdraw prior to the final assessment of response at 24 weeks. These participants will 1148 be included in the denominator for evaluation of the response rate primary endpoint. The 1149 characteristics at time of randomization for those participants without complete follow-up 1150 will be examined; however, there will be limited statistical power to detect any but major 1151 differences between these participants and those with complete follow-up. In addition, in order to assess the potential biases introduced by differential withdrawal among treatment 1152 1153 arms, a comparison of withdrawal rates and time to withdrawal will be included as an 1154 ancillary analysis to the primary endpoint comparison.

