- 1196 Profiles of symptom changes over time as collected from the symptom questionnaires and 1197 voiding logs will be compared among treatment groups using methods for longitudinal 1198 data analysis (67). These methods will include random effects regression models for 1199 continuous outcomes and GEE methods for categorical and ordinal outcomes (67). Both within- and between-participant variability in these outcomes will be carefully assessed 1200 1201 to provide pilot data for future clinical trials. For measures obtained only at baseline and one follow-up time point, change from baseline will be compared among groups using 1202 analysis of variance (ANOVA) and regression methods. When applicable, additional 1203 1204 analyses of the symptom outcomes will include evaluation of time to response defined by specific changes in symptoms (e.g. 50% drop in symptom score). Associations between 1205 longitudinal changes in secondary outcomes and the overall participant assessment of 1206 1207 improvement will be used to supplement the primary endpoint analysis and evaluate the validity of the symptom scales for assessing change. 1208
- 1209 Changes in the distribution of "worst" symptoms from baseline to 24 weeks; as recorded on the symptom ranking cards, will be evaluated using a marginal homogeneity test (64). 1210 Withdrawal rates will be compared among arms using standard methods for failure-time 1211 1212 data as described above (66). As the use of narcotic medications to control pain may provide information on the effectiveness of the treatments under study, a secondary 1213 analysis of the primary endpoint will evaluate narcotic usage. For this secondary 1214 1215 analysis, participants who initiate narcotics or increase narcotic usage 33% or more above baseline will also be considered "failures". The secondary analysis will include these 1216 1217 failures in the denominator for assessment of response rates and also compare narcotic 1218 usage among the treatment arms.
- 1219 15.5 Data Safety and Monitoring and Interim Analyses

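### The SF-36, MOS Sexual Functioning Scale and Symptom Ranking Cards have one stated post-baseline time, week 24, and no stated collection at withdrawal, so their analyses would rest on those with a week 24 form.

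*Protocol*

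**What the plan says.** **Collection.** Section 10.1.2 lists the Symptom Ranking Cards at Baseline Visit 2, together with the Health "Status Questionnaire (MOS SF-36), and the MOS Sexual Functioning Scale". Section 10.1.3 names these three instruments again only at the final week 24 visit. Its list for weeks 3, 10 and 17 has the IC Symptom and Problem Index, the Wisconsin survey, the Follow-up Symptoms form and the diaries. Section 10.1 says more loosely, after listing the visits, that participants "will be asked to complete several quality of life and symptom scale questionnaires", without naming any of the three.

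**Withdrawal.** Section 15.3 says "it is expected that up to 30% of the randomized participants may" leave before the 24-week response assessment. The global rating is covered: under 10.1.2 participants are told "that upon completion of the study, or withdrawal, whichever" is sooner, they will be asked to make the comparison with Baseline Visit 2, and 7.1 and 15.2 agree. Section 10.1.5 gives reasons for early termination but no assessments to be made then. Section 15.3 adds that people who stop treatment "will be encouraged to continue on study in order to provide complete follow-up" data. The intent-to-treat analysis is the one that "will be used for the primary comparison of treatments".

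**Analysis.** Under 15.4, for a measure with a baseline and "one follow-up time point, change from baseline will be compared among groups using" analysis of variance and regression. Change in the worst symptom, as recorded "on the symptom ranking cards, will be evaluated using a marginal homogeneity test". The repeatedly measured symptom scores go into longitudinal models.

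**The concern.** Both planned analyses need a baseline value and a week 24 value from the same person. Someone who leaves at week 8 has no scheduled occasion after baseline at which any of these three forms is completed. The pain, urgency and symptom-index scores are better placed, because their values at weeks 3, 10 and 17 can enter a longitudinal model. The primary endpoint is also protected, because a leaver counts as a failure.

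At stake are precision and interpretation. Someone who leaves because of sedation is a failure in the primary analysis and absent from the quality-of-life result. If withdrawal differs by arm, the two results could then point in different directions. A later analysis plan cannot recover forms that were never completed, so this part has to be settled in the protocol.

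**Working it through.** **Inputs.** From the protocol: 136 participants, 34 per arm (15.2), hence 68 v 68 for each factorial main effect; two-sided α = 0.05 and 80% power (15.2); withdrawal of up to 30% (15.3). Assumed, because the protocol gives no figure: how withdrawal splits between arms, and how much worse leavers would score than completers.

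**The plan's own figure.** The protocol states no sample size for these scales. Its total for the response endpoint reproduces: 72 × 1.5 × 1.2 × 1.05 = 136.08, so 136. Exact Fisher power at 36 per group for 30% v 65% is 78.6%, close to the stated 80%.

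**Precision.** With n per factor level, the detectable difference in SD units is (1.96 + 0.84) × √(2/n). This takes no account of clustering or multiplicity.

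| Without a week 24 form | With a form, of 136 | n per level | Detectable effect (SD) | Power for 0.5 SD |
|---|---|---|---|---|
| 0% | 136 | 68.0 | 0.48 | 83% |
| 10% | 122 | 61.2 | 0.51 | 79% |
| 20% | 109 | 54.4 | 0.54 | 74% |
| 30% | 95 | 47.6 | 0.57 | 68% |

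At 30%, about 41 participants have no paired score. The standard error rises by √(68/47.6) = 1.195, about 20%. An effect of 0.48 SD, detectable with 80% power at 68 v 68, then has about 65%.

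**Bias.** Suppose a fraction w of an arm leaves and leavers would score d SD worse than completers. The completers' mean exceeds the whole arm's mean by w × d. If d is the same in both groups, the bias in the comparison is d × (w1 − w0).

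- 30% v 30%: zero for any common d.
- 35% v 25%: d = 0.5 to 1.0 gives 0.05 to 0.10 SD.
- 40% v 20% (mean 30%): d = 0.5 to 1.0 gives 0.10 to 0.20 SD. The standard error is √(1/(68 × 0.6) + 1/(68 × 0.8)) = 0.207 SD, so the bias is about half to one standard error.

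The sign follows w1 − w0. Higher withdrawal on active treatment flatters the active group; higher withdrawal on placebo does the reverse.

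**The case against.** The strongest reply is that non-collection is inferred from silence. Section 10.1.3 describes scheduled visits and does not name the global rating either, although that rating is plainly taken at withdrawal. Appendix G could list the forms at close-out, and 10.1 speaks of quality-of-life questionnaires at the visits. Part of this stands: a reader might infer that leavers certainly have no score, and the documents do not establish that. But 15.4 itself provides for measures with a single follow-up point, which the SF-36 and MOS scale fit, and no available text puts these forms at withdrawal.

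A reader might also infer that the protocol defines a completers-only analysis, or errs by giving no missing-score rule. Neither follows. No such analysis set is stated; it is what remains when the form is absent. Section 15.4 calls itself an overview open to revision, and a missing-data rule for secondary scales is ordinary analysis-plan content. Its mention of regression already permits baseline adjustment, so the proposed model fixes a choice that is now open.

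Third, 30% is a ceiling, and people who stop treatment are encouraged to stay, so the loss may be smaller. Section 15.3 also examines the baseline characteristics of those without complete follow-up and compares withdrawal rates and times between arms. That would reveal the imbalance that drives any bias, but would not supply the missing scores.

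Fourth, it is tempting to say that the active arm will be flattered. Section 8.3.1 does worry about losing people to drowsiness on hydroxyzine, but 10.1.5 also lists dissatisfaction with treatment, which could raise placebo withdrawal. The direction is not settled. Nor does the fall in power breach a target, since none was set for these scales.

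**Conclusion.** The point holds as a gap in stated data collection. In the available text the three instruments have one post-baseline time, only the global rating is requested at withdrawal, and both planned analyses need a week 24 form.

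At the protocol's ceiling the comparisons would rest on about 95 of 136 participants, with the detectable main effect up from 0.48 to 0.57 SD. Under the assumed splits and deficits the bias ranges from zero to 0.20 SD, in either direction; the protocol gives no basis for choosing within that range. The conclusion assumes that Appendix G does not already schedule the forms at withdrawal. The primary endpoint and the repeatedly measured symptom scores are not affected in this way.

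**What to change.** 1. In 10.1.3 and 10.1.5, state that the SF-36, the MOS Sexual Functioning Scale and the Symptom Ranking Cards are completed at the withdrawal contact where the global rating is already requested, and at week 24 by anyone who has stopped treatment but remains on study. If Appendix G already says so, bring the text into line with it.
2. In 15.4, compare week 24 SF-36 and MOS scores with adjustment for the baseline score (ANCOVA) instead of an unadjusted change-score ANOVA. The baseline score is already collected, and adjusting for it improves precision. Add a sensitivity analysis that uses the withdrawal-contact scores, or sets leavers to no improvement in line with the primary failure rule.

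Any multiple-imputation model can be left to the analysis plan. With about 24 observed per arm at the 30% ceiling, a rich within-arm model would be fragile.

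The cost is three existing forms at a contact already foreseen, and a few lines of text. Some leavers will decline, and scores at withdrawal come from a time other than week 24, which is why they belong in the sensitivity analysis.

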#### 10.1.3 Treatment and Follow-up

819

820

821

822 823

824

825 826

827

828

Participants will return for follow-up visits at week 3 and every seven weeks following (Appendix G). At weeks 3, 10, 17, and 24 participants will complete the IC Symptom & Problem Index, the University of Wisconsin Symptom Survey, the Follow-up Symptoms form, and return the Voiding Diary and Daily Medication Diaries. The participants will receive a telephone call from the RC at weeks 1, 2, 3, 6, 14, and 20. At each scheduled contact, they will be asked about excluded/restricted medications, any possible adverse events, and initiation of IC treatments. In addition, study medication compliance will be calculated at weeks 10, 17 and 24.

829At the final clinic visit on week 24, participants will be asked to complete the830Symptom Ranking Cards, the Health Status Questionnaire (MOS SF-36), the831MOS Sexual Functioning Scale, the Patient Close-out Form, and undergo a832physical examination. Urine samples will be collected, processed, frozen and833shipped to the Core Pathology Laboratory for storage. In addition, at week 24,834LFTs, the blood-coagulation tests and platelet test will be performed (Appendix835G).

836		10.1.4 Post Treatment Period
837 838 839 840 841 842 843		Any participant requesting to continue on study medication will be provided masked study medication until the study is closed to all accrual and follow-up visits. Every 12 weeks, these participants will be asked the Follow-up Symptoms measure, IC Symptom Problem Index, University of Wisconsin Symptom Survey, and return the Voiding Diary. Adverse events, serious adverse events, addition of excluded/restricted medications or IC treatments will also be recorded.
844		10.1.5 Participant Withdrawal

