For each of the two primary comparisons (Elmiron® versus no Elmiron®, hydroxyzine 1121 versus no hydroxyzine), we desire adequate numbers of participants to detect a difference 1122 in response rates between 30% and 65% (difference of 35%). The baseline response rate 1123 1124 of 30% is based on previous IC studies and other studies suggesting that this is a typical placebo rate for symptom-related outcomes. Assuming 80% power to detect the specified 1125 difference between groups at a two-sided  $\alpha = 0.05$  level of significance using the Fisher's 1126 1127 exact test, a minimum of 72 total participants are required for the two primary comparisons. After adjustments to allow for multiple comparisons in the factorial design 1128 1129 (50% increase), clustering within Randomization Site (20% increase), and interim 1130 monitoring (5% increase), a total of 136 participants or 136/4 = 34 participants per arm 1131 will be required. Total required sample sizes for alternative response rate differences are 1132 shown in the table below.

Smaller	Larger Response Rate									
Response Rate	30%	35%	40%	45%	50%	55%	60%	65%	70%	
10%	276	196	144	112	92	76	68	56	48	
20%	1168	572	344	236	168	132	104	84	72	
30%	-	5360	1424	664	392	260	184	136	108	
40%	-	-	-	5952	1540	704	408	264	184	
50%	-	-	-	-	-	6068	1540	688	392	

1135

1133 1134

In addition, for each individual treatment arm of 34 subjects, the width of a 95%
confidence interval for adverse event and other rates will be no wider than ± 17.5%. It is
expected that these 136 participants can be accrued within approximately 10 months.
Allowing for an additional 24 weeks of follow-up on all participants, the entire study
should require 16 months for completion.

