1177 Analysis of Primary Outcome: The primary analysis comparing response rates will make 1178 use of the exact conditional test (ECT) version of Mantel-Haenszel methods to adjust for within-center clustering, as implemented within the Proc-StatXact software system (64). 1179 Secondary analyses of the primary endpoint will rely on logistic regression and 1180 generalized estimating equation (GEE) methods to evaluate whether observed 1181 differences, if any, are attributable to imbalances in prognostic factors such as baseline 1182 1183 symptom severity (65). Standard regression diagnostics will be used to assess model 1184 adequacy and examine potential outlying or influential data points. In addition, time to

response will be compared among groups using standard methods for failure-time data,
including Kaplan-Meier curves, logrank tests, and Cox proportional hazards modeling
(66).

1188 Secondary Analyses: A number of secondary analyses will be conducted both to evaluate the secondary symptom-related outcomes and to supplement the primary endpoint 1189 1190 comparison. Secondary outcomes include pain and urgency measured on the Likert scales, urinary frequency and volume measures obtained from the voiding diary, the IC 1191 Symptom and Problem Index, the University of Wisconsin Symptom Survey, the Health 1192 Status Questionnaire (MOS SF-36), and the MOS Sexual Functioning Scale. Other 1193 1194 outcomes to be used in the final assessment include withdrawal rates and the use of 1195 narcotic medications for pain control.

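### The only test named for the worst-symptom ranking compares baseline with week 24 and makes no comparison between treatment groups

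*Protocol*

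**What the plan says.** Under the secondary analyses in Protocol Section 15.4, the worst symptom from baseline to week 24, "as recorded on the symptom ranking cards, will be evaluated using a marginal homogeneity test (64"), and the sentence stops there. The secondary analyses are introduced as serving to evaluate the "secondary symptom-related outcomes and to supplement the primary endpoint" comparison.

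The cards are completed twice in the main study. Section 10.1.2 lists them at the randomisation visit ("questionnaires will also be administered: Symptom Ranking Cards, IC"), and Section 10.1.3 lists them again at week 24.

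Elsewhere in Section 15.4, symptom profiles, withdrawal rates and narcotic use are compared among groups or arms. A general rule in the preceding paragraph reads: "For measures obtained only at baseline and one follow-up time point, change from baseline will be compared among groups using" analysis of variance and regression methods.

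**The concern.** A marginal homogeneity test pairs each participant's category at baseline with the same participant's category at week 24. It asks whether the overall distribution moved. In a placebo-controlled 2 × 2 factorial trial the useful question is whether it moved differently with a drug than without it, and this test does not address that.

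Running it separately in each arm does not help. A significant result in one arm and a non-significant result in another is not a test of the difference between them.

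At stake is the use made of the ranking cards. As written, the sentence specific to them yields a p-value that reflects anything changing the ranking over 24 weeks, whether or not a drug caused it. It also yields no randomised evidence on whether either drug changes which symptom dominates.

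**Working it through.** The protocol gives no figure for this test, so there is none to reproduce. The check sets out what the test responds to and then puts sizes on it.

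**Inputs from the protocol.** 136 participants, 34 per arm (Section 15.2). Up to 30% withdrawal before week 24 (Section 15.3), so 136 × 0.70 = 95.2, about 95 paired rankings.

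**Assumptions, because the documents give no values.** Three worst-symptom categories (pain and two others), baseline shares 50/25/25%, and a 5% level. The asymptotic form of the test was simulated, with 2,000 to 3,000 trials per scenario.

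**1. The statistic.** For a 3 × 3 table of baseline (rows) by week 24 (columns), the Stuart-Maxwell form is Q = d′S⁻¹d on 2 degrees of freedom (5% critical value 5.99). Here
- dᵢ = row total i − column total i;
- Sᵢᵢ = row total i + column total i − 2nᵢᵢ;
- Sᵢⱼ = −(nᵢⱼ + nⱼᵢ).

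Treatment appears nowhere in Q.

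**2. Common shift, no drug effect.** Let every arm move from 50/25/25% to 30/35/35%. Half keep their category and the rest are redistributed 10/45/45%. The expected cell proportions are:

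| Baseline | Pain | Other A | Other B |
|---|---|---|---|
| Pain | 0.2750 | 0.1125 | 0.1125 |
| Other A | 0.0125 | 0.18125 | 0.05625 |
| Other B | 0.0125 | 0.05625 | 0.18125 |

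Using the first two categories, d = N(0.20, −0.10), S₁₁ = 0.25N, S₂₂ = 0.2375N and S₁₂ = −0.125N. Then

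Q = N × (0.04 × 0.2375 − 2 × 0.02 × 0.125 + 0.01 × 0.25) / (0.25 × 0.2375 − 0.125²) = N × 0.0070 / 0.04375 = 0.16N.

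| Paired rankings | Q at expected counts | Simulated rejection | Between-group week-24 test |
|---|---|---|---|
| 136 | 21.8 | 99.8% | 5.4% |
| 95 | 15.2 | 97.8% | 5.3% |
| 34 (one arm) | 5.4 | 57% | not applicable |

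**3. Smaller common shifts, no drug effect.** Here 15% of those with another worst symptom switch at random, and a set proportion of pain-worst participants move away. The same rates apply with and without drug.

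| Pain-worst who switch | Pooled, N = 95 | One side, N = 48 | Between groups |
|---|---|---|---|
| 7.5% (no net shift) | 4% | not above about 4% | 4.6% |
| 20% | 29% | 12% | 5.5% |
| 30% | 63% | 31% | 5.3% |
| 40% | 88% | 55% | 4.3% |

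**4. Opposite shifts by group.** Let pain be worst at week 24 in 35% of one group and 65% of the other. The pooled share is (35 + 65)/2 = 50%, equal to baseline, so the expected d is zero. The pooled test rejects in 3.7% of trials at N = 136 and the between-group test in 90.7%.

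**5. Improvement equal across symptoms.** Worst symptom is a ranking. Subtracting the same amount from every severity leaves the ranking unchanged. In a simulation with latent severities:

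| Mean change | N = 136 | N = 95 | N = 34 |
|---|---|---|---|
| −2 for all symptoms | 4.8% | 4.8% | 3.8% |
| Pain −2, others −1.5 | 68% | 50% | 18% |
| Pain −2, others −1 | 99.8% | 97.8% | 59% |

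The trigger is therefore unequal change across symptoms, not improvement as such.

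**The case against.** Four counter-arguments deserve weight.

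- **A between-group rule already exists.** The cards are completed at baseline and one follow-up, so by its wording the two-time-point rule covers them, and regression methods could include a multinomial model. This stands in part. But a nominal category has no change score to enter into analysis of variance, and the cards then receive their own sentence with a different test. An analyst would follow the specific sentence.
- **The text is provisional.** Section 15.4 calls itself an overview that may be revised, and choosing a nominal-data test is often left to an analysis plan. That lowers the severity. It does not make the point empty, because the protocol names a test rather than leaving it open.
- **The analysis may be meant as description.** Worst symptom is absent from Section 7.2 and from the secondary outcomes listed in Section 15.4, and other analyses there are not comparative. This stands, and it is why labelling the result descriptive is part of the fix.
- **The sizes are assumed.** This also stands. The rejection rates show what the test responds to, not what this trial would yield.

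A reader might infer that ordinary placebo improvement will make the test reject. Section 15.2 does expect a 30% "placebo rate for symptom-related outcomes", but that is an overall response rate and implies no change in which symptom ranks worst; step 5 shows rejection near 5% when all symptoms improve equally. Entry also requires "a pain/discomfort score of at least 4 at both Baseline" visits, with a frequency threshold too, so regression to the mean is possible. It could affect both symptoms, and simulating that selection alone, with assumed reliabilities, gave only about 5% to 10% rejection at N = 95.

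**Conclusion.** The point holds in a limited form. The one test named for the ranking cards has a null of no change over time and supplies no randomised comparison. It can reject when all arms shift alike (from about 29% to 98% at 95 paired rankings across the unequal shifts assumed here), and run pooled it can miss opposite shifts. Those figures rest on three categories, a 50/25/25% baseline split and assumed switching, none of which the documents supply.

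It would go too far to say that the protocol presents this test as evidence of efficacy. It says only that the changes will be evaluated. The severity is minor: the primary endpoint, sample size, interim analysis and expansion decision do not depend on it.

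**What to change.** Add a comparison among treatment groups that suits a nominal outcome. For each drug factor, compare week-24 worst symptom between drug and no drug, using an exact generalised Mantel-Haenszel test stratified by baseline worst symptom. A multinomial logistic model adjusted for baseline worst symptom is an alternative. Keep the baseline-by-week-24 table and the marginal homogeneity test within each arm, labelled as descriptive of change over time and not as evidence of a treatment effect.

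The cost is one sentence in Section 15.4, with no new data. The drawback is low power. At 95 completers, suppose 60% of pain-worst participants switch on drug and 30% off drug. Week-24 pain-worst shares are then 0.5 × 0.40 + 0.5 × 0.075 = 23.75% and 0.5 × 0.70 + 0.5 × 0.075 = 38.75%. A simple unstratified between-group test has about 27% power for that difference. The pooled marginal homogeneity test would reject in 94% of such trials, but would also reject in 63% if both groups switched at 30%, so its higher rate is not power to detect a drug effect.
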